Treatment period	The period from the first day of the investigational drug administration (Day 1 of Cycle 1) to the day before the first examination, observation and investigation scheduled during the follow-up period
End of follow-up period	The day on which the last (latest) examination, observation and investigation scheduled during the follow-up period is performed
Follow-up period	The period from the day of the first examination, observation and investigation scheduled during the follow-up period to the end of follow-up period
Study period	The period consists of "screening period", "treatment period" and "follow-up period"
Measurable lymphoma lesions	
 • A measurable enlarged lymph node is defined as a lesion of > 1.5 cm in greatest transverse diameter regardless of short axis measurement or > 1.0 cm in short axis regardless of greatest transverse diameter that is clearly measurable in 2 perpendicular dimensions. • A measurable extranodal mass lesion is defined as a lesion of \geq 1.0 cm in greatest transverse diameter (two times longer than the scan slice thickness). • A nodular mass within the liver or spleen is defined as a space-occupying lesion of \geq 1.0 cm in 2 perpendicular dimensions.
Tumor response	"Complete Response (CR)" and "Partial Response (PR)"
Overall Response Rate	Proportion of subjects with "CR or PR" in the evaluable subject population
Progression-Free Survival (PFS)	Time from the first day of investigational drug administration (Day 1 of Cycle 1) to the date of "progressive disease" or "relapsed disease", or the date of "death", which occurs earlier

Abbreviation/Acronym/Term	Definition
Overall Survival (OS)	Time from the first day of investigational drug administration (Day 1 of Cycle 1) to the date of "death" from any cause
Time to Response (TTR)	Time from the first day of investigational drug administration (Day 1 of Cycle 1) to the first day of tumor response observed for patients who achieved a CR or PR
Duration of Response (DOR)	Time from the first day of tumor response observed for patients who achieved a CR or PR to the date of "progressive disease" or "relapsed disease", or the date of "death" which occurs earlier
Baseline	Results at the last time point of examination, observation and investigation before the start of the first administration of investigational drug in Cycle 1

TABLE OF CONTENTS

1. BACKGROUND AND RATIONALE	1
1.1. Target Disease	1
1.2. Investigational Drug	1

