3.2.3. Medications

- (9) Patients who have used agents containing darinaparsin;
- (10) Patients who have received anticancer chemotherapy (including continuous use of oral administration or injection of corticosteroids equivalent to > 10 mg/day of prednisolone, as anticancer therapy) or anticancer immunotherapy (excluding antibody therapy) within 3 weeks before the day of subject enrollment;
- (11) Patients who have received antibody therapy (including investigational drugs) within 12 weeks before the day of subject enrollment;
- (12) Patients who have received radiotherapy within 3 weeks before the day of subject enrollment;
- (13) Patients who have received autologous hematopoietic stem cell transplant within 12 weeks before the day of subject enrollment, or patients who have received allogeneic hematopoietic stem cell transplant;
- (14) Patients who underwent major surgery (e.g., surgery requiring systemic anesthesia, craniotomy, thoracotomy, or laparotomy) within 4 weeks before the day of subject enrollment;
- (15) Patients who are participating in other clinical trials or received any investigational drug or device within 4 weeks before the day of subject enrollment;

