6. STUDY PROCEDURES

The principal investigator or sub-investigator (or designated staff) will enter the results of examination, observation and investigation specified in this Section 6, and also the dates and times for blood and urine collection, as needed, into the eCRF.

The frequent performance of such invasive examinations and medical imaging tests; such as bone marrow biopsy and CT/PET imaging test, are considered medically and ethically unfavorable. Therefore, the bone marrow biopsy, CT and PET data that are obtained from routine medical practice before obtaining the informed consent from the subject may be allowed to be used as screening data of this study; only when these invasive examinations and medical imaging tests are performed within 28 days before subject enrollment. For the use of such data, a prior consent from the subject is required. However, PET data should be taken according to the study-specific procedures that is standardized by the Central Imaging Review institution of this study.

The principal investigator or sub-investigator will be allowed to add the time points of examinations, observations and investigations as needed for the follow-up observation of AEs.

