6.14.1. Baseline Assessment

The following imaging tests and examinations will be performed during the screening period (from Day -28 to Day -1) for the assessment of lymphoma lesions present at baseline:

- Radiological assessment of tumors with contrast enhanced computed tomography (contrast-enhanced CT) image data at baseline

Slice thicknesses of ≤ 5 mm will be obtained from the area covering disease lesions in the neck (infraorbital margin) to pelvis (femoral) region. Simple CT may be acceptable in a subject with known contraindication to CT contrast agents. In case that any

inadequate CT images are obtained for any reason, CT image data by Fluorodeoxyglucose-Positron Emission Tomography (FDG-PET) may be alternatively used. The detailed procedures/conditions of contrast-enhanced CT scan are specified in a separate document.

- Radiological assessment of tumors with FDG-PET data at baseline

The area covering disease lesions in the neck (infraorbital margin) to pelvis (femoral) region will be scanned. The detailed procedures/conditions of FDG-PET scan are specified in a separate document.

- Enlargement of liver or spleen (splenomegaly and hepatomegaly) will be assessed by CT scan and palpation
- Infiltration in bone marrow will be assessed by bone-marrow biopsy (biopsy should be preferred whenever possible) or aspiration (clot sections)
- For subjects with gastrointestinal lesion: lymphoid cell infiltration will be assessed by endoscopy and biopsy
- For subjects with skin lesion: photographs of skin lesion will be taken

Based on the radiological assessment at baseline, target lesions and non-target lesions will be chosen, nodal lesions or extranodal lesions will be classified, the size in 2 perpendicular dimensions of target lesions will be measured, the sum of the products of the greatest diameters (SPD) of target lesions will be calculated, and the results of FDG-PET results will be assessed.

Target and non-target lesions will be selected in consideration of reproducibility at the subsequent assessment of radiographic tumor response in the study. When nodular lesions in the liver or spleen are selected as target lesions or non-target lesions, nodular mass in the spleen will be classified as nodal lesions; and nodular mass in the liver will be classified as extranodal lesions. The enlargement of liver and spleen will be separately assessed including assessment by palpation.

<Target lesion>

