- Up to 6 measurable lesions will be selected, for both enlarged lymph nodes and extranodal mass lesions. Larger lesions in order of the long diameter are preferred. See Inclusion Criteria [See Section 3.1 (5)] for the definition of measurable lesions.
- If one or more measurable lesions are found in a single lymph node region or a single organ, except for the lesion with the greatest long diameter, lesions should be selected from disparate regions of the body if possible.
- Any measurable lesions in the mediastinal or the retroperitoneal sites should be selected.

<Non-target lesion>

- All other sites of disease present at baseline and not classified as target lesions will be classified as non-target lesions, including any measurable lesions that are not chosen as target lesions.

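### A pre-consent baseline scan can pre-date the last prior chemotherapy or radiotherapy by about 5 to 6 days, and no rule or analysis detects it

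*Protocol*

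**What the plan says.** **Baseline window.** Protocol Section 6 says that bone marrow, CT and PET data "obtained from routine medical practice before obtaining the informed consent from the subject may be allowed to be used as screening data of this study", but "only when these invasive examinations and medical imaging tests are performed within 28 days before subject enrollment". PET must also follow the study's standardised procedure. Section 6.14.1 states a different window: "The following imaging tests and examinations will be performed during the screening period (from Day -28 to Day -1)". Section 6.14.3 uses the same Day -28 to Day -1 window for images sent to central review.

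**Washout.** Section 3.2.3 counts back from enrollment.
- Exclusion 10 covers chemotherapy, including continuous corticosteroids above 10 mg/day prednisolone equivalent given as anticancer therapy, and "anticancer immunotherapy (excluding antibody therapy) within 3 weeks before the day of subject enrollment".
- Exclusion 12 covers "Patients who have received radiotherapy within 3 weeks before the day of subject enrollment".
- Exclusion 11 is longer: "Patients who have received antibody therapy (including investigational drugs) within 12 weeks before the day of subject enrollment".

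**Other rules.**
- The ban on other anticancer therapy in Section 5.5.2 runs from the day of consent.
- The Study Glossary defines baseline as "Results at the last time point of examination, observation and investigation before the start of the first administration of investigational drug in Cycle 1".
- Inclusion criterion 4 asks for at least one prior regimen, not for imaging or progression after the most recent one.
- The target-lesion rules in Section 6.14.1, such as "Any measurable lesions in the mediastinal or the retroperitoneal sites should be selected", do not mention lesions treated after the scan.
- The SAP (Sections 5.1 and 11.1) has no rule or sensitivity analysis for a baseline that pre-dates the last prior treatment.

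**The concern.** The scan may be older than the washout is long, and nothing requires the scan to come after the last treatment. A patient could be scanned in routine practice, receive a last dose of chemotherapy, anticancer corticosteroid or radiotherapy a few days later, then consent and enroll with that scan as baseline.

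The primary endpoint is best overall response up to Cycle 6 measured against this baseline. A partial response needs at least a 50% fall in the sum of products of diameters (SPD). The trial has one arm and a fixed 10% threshold, so no control group would show the same carry-over. Central review reads the same screening images and cannot correct their timing. Along this path, the error favours the drug.

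**Working it through.** **1. Day count** (enrollment = E)

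| Step | Section 6 window | Day -28 to Day -1 window |
|---|---|---|
| Earliest baseline scan | E-28 | Day -28. Enrollment falls within screening, so it is at latest Day -1, and Day -28 is then E-27 |
| Latest permitted chemotherapy or radiotherapy (day 21 read as excluded) | E-22 | E-22 |
| Largest lag from scan to treatment | 28 - 22 = 6 days | 27 - 22 = 5 days, only if dosing starts the day after enrollment |

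If treatment exactly 21 days before enrollment is read as permitted, each lag grows by one day. The overlap concerns pre-consent scans only, because after consent the other therapies are banned. Antibody therapy and autologous transplant (12 weeks) and surgery and investigational agents (4 weeks) leave no gap.

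**2. The plan's own sample size** (Protocol Section 9.2: threshold 10%, expected 25%, one-sided 5%, power 90%)

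The rule is the smallest r with P(X ≥ r | n, 0.10) ≤ 0.05, and n is the smallest size at which this r gives power of at least 90%.
- n = 55, r = 10: P(X ≥ 10 | 55, 0.10) = 0.044 and P(X ≥ 10 | 55, 0.25) = 0.911.
- n = 54, r = 10: power is 0.899, just short.

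The stated 55 is reproduced. The lower 90% Clopper-Pearson limit gives the same cut-off: 10.2% at 10/55 and 8.8% at 9/55. If all 65 planned subjects are evaluable, the cut-off is 12 and the false-positive rate is 0.026.

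**3. Effect of k certain carry-over responders when the true rate is 10%**

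Formula: P(X ≥ r - k | n - k, 0.10).

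| k | n = 55, r = 10 | n = 65, r = 12 |
|---|---|---|
| 0 | 4.4% | 2.6% |
| 1 | 8.6% | 5.2% |
| 2 | 15.6% | 9.5% |

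One responder in 55 is 1/55 = 1.8 percentage points of response rate.

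**4. Effect with assumed frequencies**

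The documents give neither the share f of subjects affected nor the share q of those who show a carry-over response. The apparent rate is 0.10 + 0.90 × f × q.

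| f | q | Apparent rate | False-positive rate, n = 55 | n = 65 |
|---|---|---|---|---|
| 2% | 20% | 10.36% | 5.4% | 3.4% |
| 5% | 10% | 10.45% | 5.7% | 3.6% |
| 5% | 30% | 11.35% | 8.9% | 6.0% |
| 10% | 50% | 14.5% | 27.0% | 22.6% |

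All four pairs are assumptions. The last two are shown only to mark how far the result depends on them.

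**5. Timing of the first response scan**

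Cycle 3 Day 15 is study day 2 × 21 + 15 = 57, that is 56 days or 8 weeks after Day 1. If the last treatment was at E-22 and dosing started the day after enrollment, the first scheduled scan falls 22 + 1 + 56 = 79 days, about 11 weeks, after that treatment.

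**The case against.** Most of the case against concerns size, and much of it stands.

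- **Several events must coincide.** The scan must sit at the far edge of its window, treatment must end within days of it, and at least 3 weeks without treatment must follow. This is probably uncommon.
- **Carry-over must last and be large.** It must still show as at least a 50% fall in SPD with no new sites about 11 weeks later, in a disease that Section 1.1 describes as progressing month by month. Subjects who stop early are scanned sooner. Irradiating one lesion produces a partial response only if that lesion dominates the SPD.
- **The imaging rules give partial protection.** PET must follow the study procedure, and Section 6.14 fixes the devices. A routine PET that fails these conditions would be repeated, and a repeat after consent would become the baseline. These rules do not set the order of scan and treatment, and a valid routine CT need not be repeated.
- **The SAP gives partial visibility.** Section 11.1 splits response by outcome of the most recent therapy, with an unknown category. It does not identify subjects by scan date.
- **The direction is not only upward.** An early scan also misses growth before dosing, which lowers measured response. The net effect is not known.

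A reader might infer that a scan at E-28 meets every rule and leaves a full week of overlap, since 28 - 21 = 7. The documents do not support that plainly: with enrollment at latest on Day -1, E-28 is Day -29 or earlier, outside the window in Sections 6.14.1 and 6.14.3. Seven days also requires treatment on day 21 to be permitted.

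A reader might also infer a false-positive rate of 9% to 27%. That needs 5% to 10% of subjects affected and 30% to 50% of those responding by carry-over. No document figure supports either input, and the second exceeds the 25% response rate expected of SP-02L itself.

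What remains is that no provision in either document places the baseline after the last prior treatment.

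**Conclusion.** The gap is real but narrow: up to about 6 days under Section 6, or about 5 days under Sections 6.14.1 and 6.14.3, and only for pre-consent data. It covers chemotherapy including anticancer corticosteroids, non-antibody immunotherapy and radiotherapy.

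The documents show that misattribution is possible, not that it is frequent or that the response rate is inflated overall. The test is nonetheless sensitive to small counts: a single carry-over responder roughly doubles the false-positive rate at either sample size (4.4% to 8.6% at 55, 2.6% to 5.2% at 65). With low assumed inputs (5% affected, 10% of those carrying over), the rate at 55 is 5.7%.

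Severity is minor to moderate. It is not a must-fix point, but it is worth settling before the primary analysis because recorded dates can answer it.

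**What to change.** **SAP (main remedy).**
- For each subject, compare the baseline CT, PET and bone marrow dates with the end date of the last prior chemotherapy, non-antibody immunotherapy, anticancer corticosteroid or radiotherapy.
- List subjects whose baseline pre-dates that treatment.
- Report one sensitivity response rate with its 90% confidence interval, counting any responders among them as non-responders.
- First confirm that radiotherapy dates are captured. Protocol Section 6.2 lists periods for prior medication only, while SAP Section 13 lists prior radiation.

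If no subject is affected, one sentence in the report closes the question.

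**Protocol (any further enrollment).** State in Sections 6 and 6.14.1 that pre-consent imaging or marrow data may serve as baseline only if obtained after the last such treatment, and that otherwise the screening assessment already scheduled in Section 6.14.1 is used. Antibody therapy need not be named, given its 12-week washout. Reconcile the window in Section 6 with that in Sections 6.14.1 and 6.14.3.

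This edit may come late. Version 3.5 is dated January 2020, and survival surveillance of up to 2 years from first dose is planned to end in December 2021, so planned accrual was probably near its end.

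**Cost.** One listing and one sensitivity row in the SAP. In the protocol, a few patients would lose the exemption and have the screening scan that is already scheduled. The sample size and cut-off do not change.

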6.1. Subject Background

The following information regarding the subject background will be collected upon obtaining consent from the subject.

- Date of birth
- Sex
- Ethnic background: ethnic group, race

6.2. Medical History of Primary Disease

The following information regarding the medical history of primary disease will be collected on any day between Day -28 to Day -1 of the screening period.

- Histopathological diagnosis (histopathological subtype) of primary disease; made at the investigational site
- Date of diagnosis
- Clinical stage by the Ann Arbor Classification at a screening visit
- Prognostic risk group by International Prognostic Index (IPI) at a screening visit
- Prognostic risk group by Prognostic Index for T-cell lymphoma (PIT) at a screening visit
- Clinical symptoms caused by the primary disease (clinical symptoms associated with primary disease)
- Prior medication: name of regimen or drugs, periods of medication and responses to medication as needed

6.3. Lymphoid Tissue Specimen Submission

Upon the subject's enrollment, 15 unstained tissue specimens taken from the lymphoid tissue (lymph nodes, in principle); on which a local pathological diagnosis of primary disease is confirmed, will be submitted to the central laboratory of each country or region. Unstained tissue specimens will be prepared on coated glass slides; formalin-fixed paraffin-embedded $\leq 5 \mu\text{m}$ -thick sections will be mounted on the coated glass slides. If prior biopsies were performed multiple times before subject enrollment, the principal investigator or a pathologist at each investigational site should submit the tissue specimens that are considered most valid basis for a local pathological diagnosis; either of the biopsy samples taken at an initial onset or at a relapse of disease are acceptable. According to the requests from the Pathological Review Committee, supplemental submission of unstained or stained tissue specimens may be requested.

If less than 15 unstained tissue specimens can be submitted, as many unstained tissue specimens as possible and the previously-stained tissue specimens; that should include the specimen stained by hematoxylin and eosin staining, supporting the local pathological diagnosis should be submitted. The stained tissue specimens will be borrowed from the investigational site in accordance with each investigational site's procedures.

Details of the procedure for tissue specimen submission to the central laboratory of each country or region are specified in a separate document. At the central laboratory, the unstained tissue specimens will be stained at the direction of the Pathological Review Committee, and then all of tissue specimens will be submitted to the Pathological Review Committee.

6.4. Performance Status

Performance status will be determined according to ECOG performance status scale [See Appendix 1] on any day during the screening period (Day -28 to Day -1).

6.5. Medical History

The following information regarding the past and/or concurrent diseases including drug sensitivity and allergy will be collected on any day during the screening period (Day -28 to Day -1):

- Diagnosis or symptom, and date of diagnosis
- Drug sensitivity or allergy: if applicable, name of drug or allergen, severity

Before the start of the first dosing of investigational drug on Day 1 of Cycle 1, whether or not the concurrent disease is ongoing at the start of investigational drug administration will be assessed.

6.6. Pregnancy Status

For subjects other than male and postmenopausal or surgically sterilized female subjects, a urine human chorionic gonadotropin (hCG) pregnancy test will be conducted on any day

during the screening period (between Day -28 to Day -1) and also before the start of investigational drug administration on Day 1 of each cycle. “Menopause” is defined as being at a state of absence of menstrual periods for at least 12 months, excluding the cases of absent menstruation due to a medical reason such as medication.

Throughout the study period, the principal investigator or sub-investigator (or designated staff) should confirm that the subject or subject’s partner is not pregnant.

6.7. Height and Weight Measurement

Body height (cm) and weight (kg) will be measured on any day during the screening period (between Day -28 to Day -1). To determine the dose (mg) of the investigational drug, a body surface area (BSA: m²) will be calculated using the DuBois’s formula, based on the subject’s height and weight. [See Section 5.3.1]

The subject’s body weight will be also measured before the start of investigational drug administration on Day 1 of each cycle. If the weight changes by $\pm 10\%$ compared to the weight measured at the screening visit, BSA will be recalculated using the DuBois’s formula to adjust the dose. [See Section 5.3.1]

6.8. Physical Examination

At each time point shown in Table 2, the principal investigator or sub-investigator will perform a physical examination. At the physical examination, careful assessment for neurological and mental status should be performed, especially for the following findings.

- Findings suggestive of cranial nerve abnormalities
- Findings suggestive of sensory abnormalities
- Findings suggestive of motor abnormalities
- Findings suggestive of coordination stance / gait abnormalities
- Findings suggestive of reflexes abnormalities
- Findings suggestive of mental status abnormalities

Table 2: Time Points of Physical Examination in Cycle

	Time Point	Time Window
Screening Period	Any day between Day -28 and -1	
Treatment Period	Day 1; before the investigational drug administration	Before the start of infusion
	Day 5; after the investigational drug administration: Cycle 1 only	After the end of infusion
	Day 8	± 2 days (Day 6 - 10)
	Day 15	+ 6 days (Day 15 - 21)
Follow-up Period	Day 22	+ 7 days (Day 22 - 29)

6.9. Vital Sign and Arterial Oxygen Saturation Measurement

Systolic and diastolic blood pressure (mmHg), pulse rate (beats per minute), body temperature (°C), and percutaneous arterial oxygen saturation (SaO₂) (%) by using a pulse oximeter will be measured, at the time points shown in Table 3.

Table 3: Time Points of Vital Sign and Arterial Oxygen Saturation Measurement in Cycle

	Time Point	Time Window
Screening Period	Any day between Day -28 and -1	
Treatment Period	Day 1; before investigational drug administration	Before the start of infusion
	Day 5; after investigational drug administration: Cycle 1 only	Within 60 minutes after the end of infusion
	Day 8	± 2 days (Day 6 - 10)
	Day 15	+ 6 days (Day 15 - 21)
Follow-up Period	Day 22	+ 7 days (Day 22 - 29)

